1. PURPOSE OF THE STUDY AND BACKGROUND

1.1. Purpose of the study

Primary Aim

The primary outcome of this study is to determine the minimal dwell time needed for adequate detection of Cysview avid tumors using protoporphyrin IX (PpIX) near infrared fluorescence (NIRF).

Secondary Aim

To determine in vivo the ratio of intensity of near infrared fluorescence (NIRF) signal arising from the tumor compared to that arising from normal tissue as a function of dwell time.

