3.2. Inclusion and Exclusion Criteria

a) **Inclusion Criteria:**

- Diagnosis of bladder mass on office cystoscopy suspicious for malignancy, either newly diagnosed or a recurrent tumor
- Planned transurethral resection of bladder tumor in the operating room
- Men or women (age 18 or older)
- Any racial or ethnic origin
- Ability to give informed consent

b) **Exclusion Criteria:**

- Pregnancy
- Nursing mother
- Diagnosis of porphyria
- Gross hematuria
- BCG immunotherapy or intravesical chemotherapy within the past 90 days
- Known hypersensitivity to hexaminolevulinate or any derivative of aminolevulinic acid

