5. METHODS AND STUDY PROCEDURES

The study will be a single center prospective nonrandomized trial of an investigational imaging technology. All patients will undergo investigational imaging and the concomitant standard of care, i.e. transurethral resection of bladder tumor (TURBT). Patients with suspected bladder cancer on cystoscopy will be enrolled to have subsequent intraoperative intravesical administration of Cysview and NIRF cystoscopy prior to TURBT.

Ten patients will be recruited to demonstrate the feasibility of using this NIRF imaging system at shorter intravesical instillation durations (Cysview™ dwell time). The instillation duration will be 10, 5, or 2.5 minutes in this patient series. The subject will be anesthetized, positioned, prepped, and draped for the white light TURBT. A catheter will be passed, Cysview instilled, and the catheter clamped for the assigned dwell time. It will then be unclamped after the dwell time designated, Cysview will be

allowed to drain out, the catheter removed, and cystoscopy performed. The cystoscope is inserted and imaging of the entire bladder commences while recording both color and near-infrared image streams (movies and periodic stills). This initial survey that includes catheterization of the bladder under anesthesia, instillation of Cysview, dwell time as indicated and subsequent evaluation with the color and near-infrared imaging for research purposes. Cysview with blue light cystoscopy has been indicated to be desirable at the time of TURBT but it is not standard of care; it is an optional procedure to increase detection and decrease recurrence. A useful dwell time for Cysview before NIRF imaging will be identified in this study; an effort will be made to minimize the interval between administration and imaging.

The procedure and all study portions will be performed by the subject's surgeon. During the procedure, the bladder will initially be examined in a systematic meridian fashion. Suspicious tumors identified by white light only, NIRF only, and both will be identified. If fluorescence is detected in 3/3 subjects at a given dwell time, the study will continue to shorter dwell times. The initial 3 subjects will have 10 min dwell duration, followed by 5 min and 2.5 min. If fluorescence is not detected in 3/3 subjects at any time period, the study will not progress to shorter dwell times. If no fluorescence is visualized after 10 minutes, we will not proceed to a longer dwell time.

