5.2. Efficacy Assessments

This initial series is designed solely to demonstrate that tumors identifiable under white light will be seen to fluoresce in the near-infrared spectrum after relatively short dwell times. We will document detectability of individual tumors under white light and NIRF at short intervals after Cysview instillation.

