- False positive fluorescence may result from scope trauma from a previous cystoscopic examination and/or bladder inflammation [see Warnings and Precautions (5.3)].
- Malignant lesions may not fluoresce following Cyview administration, particularly if the lesions are coated with necrotic tissue. Blue light may fail to detect T2 tumors which have a tendency to be necrotic on the surface, and necrotic cells generally do not fluoresce [see Warnings and Precautions (5.3)].
- When performing the blue light cystoscopy, avoid prolonged blue light exposure. Studies have not evaluated the potential for adverse effects from blue light. In the controlled clinical trial, the cumulative blue light exposure from bladder mapping did not exceed 12 minutes and checking for complete tumor resection under blue light did not exceed 8 minutes for any patient [see Clinical Studies (14)].

Perform biopsy and/or resection of suspicious lesions by transurethral resection of the bladder (TURB) only after completing white and blue light cystoscopic examination with bladder mapping. Using standard cystoscopic practice, obtain biopsies of abnormal areas identified during either white or blue light examination and perform resections. Always check for the completeness of the resections under both white light and blue light before finishing the TURB procedure.

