5.2 Failed Detection
 Cyview may fail to detect some bladder tumors, including malignant lesions. Cyview is not a replacement for random biopsies or any other procedure usually performed in the cystoscopic evaluation for cancer. In the controlled clinical trial, Cyview failed to detect 10% of lesions confirmed as malignant within the study drug group [see Clinical Studies (14)]. Do not perform cystoscopy with blue light alone as malignant lesions can be missed unless the bladder is initially examined under white light [see Dosage and Administration (2.5)].

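### The primary aim is about Cysview avid tumors, but the trial assesses tumors seen under white light, so a dwell level that fails cannot be attributed to too short a dwell

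*Combined protocol and SAP*

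**What the plan says.** The primary aim (1.1) is to determine the "minimal dwell time needed for adequate detection of Cysview avid tumors". Avidity is not defined there, and the term does not return in eligibility, assessments, the step rule or the analysis.

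Subjects enter (3.2) on "Diagnosis of bladder mass on office cystoscopy suspicious for malignancy, either newly diagnosed or a recurrent tumor". No histology or earlier fluorescence examination is required. Section 5.2 describes the series as "designed solely to demonstrate that tumors identifiable under white light will be seen to fluoresce in the near-infrared spectrum" after short dwells, and 13.2 likewise takes tumors located on the white-light image and looks for them on the fluorescence image.

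The step rule in Section 5 reads: "If fluorescence is detected in 3/3 subjects at a given dwell time, the study will continue to shorter dwell times". The next statement on stopping is: "If fluorescence is not detected in 3/3 subjects at any time period, the study will not progress to shorter dwell times". Section 5 adds: "If no fluorescence is visualized after 10 minutes, we will not proceed to a longer dwell time". Section 8.3 words the step differently, as fluorescence being adequate, without defining adequate.

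The package insert in Appendix 2 warns (its 2.5): "Malignant lesions may not fluoresce following Cyview administration, particularly if the lesions are coated with necrotic tissue". It names T2 tumors as prone to this. Its 5.2 reports that "Cyview failed to detect 10% of lesions confirmed as malignant within the study drug group".

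**The concern.** The population named in the aim is not the population measured. No blue-light examination, labelled 60-minute dwell or other reference is scheduled, and the dwell is never extended past 10 minutes. Pathology is collected and can show whether a lesion is malignant, but not whether it takes up the agent. A subject in whom nothing fluoresces therefore has several possible explanations, of which too short a dwell is only one.

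The step rule makes no allowance for this. If 3/3 is needed to continue, one subject whose lesion would stay dark at any dwell halts the descent. The error runs one way: a non-avid or benign lesion can make a dwell look inadequate but cannot make it look adequate. Section 2.2 says the pilot is to supply the dwell time for later NIRF studies, so an inflated minimum would carry forward into them.

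**Working it through.** **The plan's own figure.** Section 13.1 takes blue-light sensitivity as better than 0.9 and gives a probability below 0.001 of failing to detect the tumors in three subjects. At 0.9 this is (1 − 0.9)^3 = 0.1^3 = 0.001, so it reproduces. It is the chance of missing all three subjects. Under a rule that needs 3/3 to continue, the relevant event is at least one miss: 1 − 0.9^3 = 0.271.

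**Inputs.**
- Three subjects per level at 10, 5 and 2.5 minutes (Sections 5 and 8.3).
- q, the share of subjects with no avid lesion. The documents do not give it, so it is an assumption. The starting value of 10% is the insert's lesion-level figure for blue light, used here as a subject-level proxy.
- NIRF is taken to detect every avid lesion at every dwell, and subjects are taken as independent. Any stop is then due to q alone.

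**If continuing needs 3/3.** A level passes with probability (1 − q)^3. The 2.5-minute level is reached only if the first two levels pass, so P(never reached) = 1 − (1 − q)^6.

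| Assumed q | Stop after 10 min, 1 − (1 − q)^3 | Never reach 2.5 min, 1 − (1 − q)^6 |
|---|---|---|
| 1% | 3% | 6% |
| 5% | 14% | 26% |
| 10% | 27% | 47% |
| 20% | 49% | 74% |
| 30% | 66% | 88% |

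The 1% row corresponds to two independent lesions per subject, each non-avid with probability 10%, where one fluorescing lesion is enough for the subject to count: 0.1 × 0.1 = 0.01. The 20% and 30% rows allow for benign masses, which 3.2 admits.

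**If stopping means 0/3.** A level stops the study with probability q^3. At q = 10% this is 0.001, and P(never reach 2.5 min) = 1 − (1 − 0.001)^2 = 0.002, or 0.2%.

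**What a result can say.** Setting false fluorescence aside, a tumor that fluoresces has shown its avidity by doing so, and a level passing 3/3 is evidence about avid tumors. Only the failing level is ambiguous, and it is the failing level that would turn an adequate dwell into a minimal one.

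**The case against.** Several points on the other side stand.

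- The operative population is clear from 5.2 and 13.2. If avid is loose wording for bladder tumors in general, the mismatch with 1.1 is editorial. The ambiguity of a failing level remains.
- The size depends on how the stop sentence is read. It can mean 0/3, and the calculation in 13.1 fits only that reading. Against this, the preceding sentence makes 3/3 the condition to continue, and no other rule covers 1/3 or 2/3. Section 8.3 adds a judgement of adequacy that fits neither exactly. Both readings therefore have to be shown.
- The 10% is a per-lesion miss rate for blue light at labelled use, not a subject-level rate of non-avidity. Section 1.2 describes multifocal disease, and the rule counts subjects. It also reports ex vivo detection of PpIX at 0.01 rather than 1 microgram per milliliter, so some blue-light misses may be limits of the detector. Both considerations lower q, while benign masses raise it.

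Three stronger readings are tempting and are not supported. A reader might infer that the aim cannot be answered at all, but passing levels do inform it. A reader might take 1 − 0.9^9 = 61% as the risk of a false stop, but that figure includes failure at 2.5 minutes, where no shorter level is left to lose. A reader might infer that a failed level will be reported as too short a dwell. The documents say only that the study does not go shorter, and 13.2 is silent on how a failed level is to be concluded.

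**Conclusion.** The point holds in a limited form. The aim names avid tumors, the trial assesses white-light-visible ones, and nothing planned separates a non-avid or benign lesion from insufficient dwell when a level fails. Any resulting bias in the apparent minimal dwell is upward.

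Under the 3/3 reading with otherwise perfect NIRF, the chance of never reaching 2.5 minutes is 47%, 26% or about 6% when 10%, 5% or 1% of subjects have no avid lesion. Under the 0/3 reading it is about 0.2% at 10%. These figures rest on an assumed q, on independent subjects and on a choice between readings that the documents leave open. They show that the problem may be large or negligible, not which it is. The limit on what a failing level can conclude holds under either reading.

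**What to change.** - In 1.1, replace the reference to Cysview avid tumors with the population that 5.2 and 13.2 already assess: tumors visible under white light. Do not add pathology confirmation to this definition, because neither the step rule nor 5.2 requires it and a new mismatch would follow.
- In 13.2, state that a failing level is concluded as *not shown adequate (non-avid or benign lesion, or insufficient dwell)* and not as too short. State also that the last passing level is the shortest dwell shown adequate, not the minimum needed.
- Report detection at each level for all subjects and, as a supportive result, for those with malignancy on the pathology already collected. For each subject with no fluorescing lesion, list the pathology and any surface necrosis visible on the video.
- Reconcile the continuation and stopping wording in Sections 5 and 8.3 with the calculation in 13.1, so that one rule is stated and the probability quoted belongs to it. Which rule applies is for the investigators to settle.

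The first three changes do not alter the chance of stopping; they prevent a stop from being read as a finding about dwell that the data cannot support. The cost is a narrower claim and a small addition to the Appendix 3 form, which has no field for surface necrosis. No procedure or subject is added.

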1.2. Background

Bladder cancer is the fifth most commonly diagnosed solid malignancy in the United States, with patients experiencing multifocal occurrences/recurrences even after seemingly successful treatment of non-muscle invading urothelial cancer. There is level 1 evidence that more complete tumor eradication results in patients experiencing fewer recurrences [1, 2]. Bladder cancer is the most costly malignancy to treat over the lifetime of patients in large part because of the need for multiple re-treatments and surgeries as well as lifelong endoscopic surveillance [3]. Thus, a practical way to improve tumor detection and removal will not only benefit individual patients but also should reduce the overall cost of managing this malignancy.

One method that improves the completeness of transurethral resection of bladder tumors (TURBTs) utilizes intravesical administration of the hematoporphyrin derivative Cysview™ (brand name Hexvix™ elsewhere) to detect tumors not readily visualized with standard white light cystoscopy. Tumor lesions are visualized intra-operatively by shining a blue light throughout the bladder that excites the resultant intracellular PpIX to emit red fluorescence; tumor cells exhibit a lower clearing rate of PpIX because of altered catabolism and transport [4-6], thus it accumulates and permits differential visualization.

Standard of care at UR for diagnosis of bladder tumors consists of white light cystoscopy only in office and then in OR where tumor is biopsied or resected. Fluorescence (blue light cystoscopy) is rarely done in large part because it requires preoperative catheter passage and drug (Cysview) instillation for 60 minutes before surgery (causes patient discomfort) and the actual operation is lengthened. While this technique is efficacious, it requires expensive special equipment, a need to examine the bladder under both white to blue light repeatedly during the case, and the solution (Cysview™) must be instilled 60 minutes before the procedure via a catheter. This inconvenient requirement leads to delay and greater expense for the facility as well as prolonging patient discomfort and apprehension. For these reasons, blue light cystoscopy has not been as widely adopted as one might expect given its clear benefits [1, 2].

We hope to eliminate the obstacles to better care by employing new and more sensitive imaging technologies that should enable more rapid tumor identification and a reduction in bladder dwell time. Agent administration could be done in the operating room just minutes before cystoscopy is performed. We will achieve this by using highly sensitive imaging technologies similar to those used in astronomy to detect near infrared fluorescence (NIRF); this imaging system will detect NIRF emitted by PpIX. Note that conventional blue light cystoscopy detects the red fluorescence emitted by PpIX. This enables two significant advances. First, NIRF can be elicited by white light excitation alone, so there is no need to use separate blue light excitation. Second, the white light image can be simultaneously acquired (viewed and/or recorded) with the NIRF image, so there is no need for switching between the blue light and the white light imaging modes as in conventional blue light cystoscopy.

Thus, this new technology will obviate the need for pre-anesthetic urethral catheterization, the hour wait in the pre-anesthetic area. This reduction in dwell time is made possible by the increased sensitivity of NIRF imaging to PpIX fluorescence. We have found ex-vivo the NIRF imaging is well over 10 times more sensitive to Cysview fluorescence than standard blue light cystoscopy. Ex-vivo preliminary studies have shown that blue light cystoscopy can detect PpIX concentrations 1 microgram per milliliter. In contrast, NIRF imaging was able to detect PpIX concentrations down to 0.01 microgram per milliliter, a 100 fold difference (Appendix 4). In addition, as this imaging technology utilizes existing conventional white light cystoscopes, it also averts the requirement for current costly and single purpose blue light generating equipment that cannot be used for other endoscopic procedures.

Many large tumors are readily seen with white light, and we expect to visualize large tumor fluorescence in a few minutes with the new system.

2. STUDY DESIGN

2.1. Overview

The study will be a single center prospective nonrandomized trial of an investigational imaging technology. All patients will undergo investigational imaging and concomitant standard of care transurethral resection of bladder tumor (TURBT). Patients with suspected bladder cancer on cystoscopy will be enrolled to have subsequent intraoperative intravesical administration of Cysview and NIRF cystoscopy immediately prior to TURBT.

2.2. Rationale for Study Design

Although studies have evaluated optimal dwell time for Cysview fluorescence when cystoscopy is performed under blue light, the optimal dwell time for NIRF visualization has not been determined. Prior to conducting randomized studies comparing efficacy of NIRF and blue light we must first establish that a useful and short dwell time can in fact be used successfully. This pilot study will allow us to identify a dwell time for subsequent NIRF cystoscopy studies.

[figure not shown]
Because from a practical point of view, that is the longest time period we want to prolong surgery with a product that should equal or improve on current blue light cystoscopy. We use blue light very selectively now for these reasons: The Dwell study and the subsequent research that comes from it – should permit avoidance of the pre-op catheterization and significantly shorten the procedure. We have found ex-vivo the NIRF imaging is well over 10 times more sensitive to Cysview fluorescence and should have no problem with visualization at 10 minutes.

2.3. Rationale for Dosage

Intravesical instillation of 100 mg Cysview (hexaminolevulinate hydrochloride) will be performed via foley catheter at the initiation of the procedure. Although NIRF is more sensitive than blue light cystoscopy, we will use the current FDA approved dose. Cysview has a favorable safety profile at this dose.

2.4. Equipment

This protocol relies on intravesical administration of an FDA-approved agent for bladder cancer detection (Cysview™) that fluoresces upon illumination with an FDA-approved cystoscopic white light source. Standard light sources emit near-infrared wavelengths that would interfere with detecting NIRF, so the cystoscopy light source is filtered to block these wavelengths and thus improve the signal to noise ratio. A standard (FDA-approved) cystoscope is introduced into the bladder and used to guide resection of any detected tumors, i.e. Trans Urethral Resection of Bladder Tumors (TURBT). *Color and near-infrared image streams will be recorded.* The surgeon will be able to display white light images, white light images with pseudocolor highlighting the near-infrared fluorescent tumor, a NIRF image, or a combination of images.

3. CHARACTERISTICS OF THE RESEARCH POPULATION

3.1. Subject Characteristics

a) **Number of Subjects:**

We will enroll 20 subjects to get 10 evaluable subjects in the study. It is expected there may be a high withdrawal rate due to the availability of the study team to all be present on the subject's surgery date.

b) **Gender and Age of Subjects:**

Male and female patients who are 18 years or older will be included. Cysview is equally efficacious and safe across both sexes. There is no scientific or medical justification to restrict inclusion of the adult population further by age.

c) **Racial and Ethnic Origin:**

There is no restriction of or subject population based on racial or ethnic grounds.

d) **Vulnerable Subjects:**

No vulnerable subjects will participate in this study.

3.2. Inclusion and Exclusion Criteria

a) **Inclusion Criteria:**

- Diagnosis of bladder mass on office cystoscopy suspicious for malignancy, either newly diagnosed or a recurrent tumor
- Planned transurethral resection of bladder tumor in the operating room
- Men or women (age 18 or older)
- Any racial or ethnic origin
- Ability to give informed consent

b) **Exclusion Criteria:**

- Pregnancy
- Nursing mother
- Diagnosis of porphyria
- Gross hematuria
- BCG immunotherapy or intravesical chemotherapy within the past 90 days
- Known hypersensitivity to hexaminolevulinate or any derivative of aminolevulinic acid

3.3. Discussion of Subject Population

The inclusion/exclusion criteria will be representative of the population that would benefit from reduced Cysview dwell time provided by NIRF cystoscopy. Patients will be excluded based upon the known contraindications for Cysview.

4. SUBJECT IDENTIFICATION, RECRUITMENT AND CONSENT

4.1. Method of Subject Identification and Recruitment

Subjects will be identified through eRecord or clinic schedules by the study team and will be recruited from the clinical offices in the Urology Department at the University of Rochester.

4.2. Process of Consent

A member of the study team with routine access to all UR Urology patients will identify potential subjects via eRecord or clinic schedules. Once a potential subject is identified and the urologist notified, the study team will introduce the study at a scheduled clinic visit and check for interest in participation. If interested, eligible subjects may be enrolled at this visit. If potential subjects wish to take the consent form home to read and review with family or friends, a member of the study team will call the patient to check their interest in participation and answer any questions they may have about the study. Informed consent will then be obtained by a member of the study team at their pre-operative visit (see Schedule of Activities – Appendix I).

Subjects will be reminded that they can elect not to participate without risking loss of any present they would normally receive. Any questions the subject may have will be answered. A copy of the signed consent form will be given to the subject and the original consent form will be placed in the research record. All research records will be accessed by the study team and stored in a locked office of the study team. Consent will be obtained in a private setting with a closed door to ensure privacy.

